Refitting contact lens dropouts into a modern daily disposable
contact lens

Study Protocol & Statistical Analysis Plan

NCT 05239494

December, 13th 2021

[name], OD, Associate Professor, Principal Investigator
University of Alabama at Birmingham
Birmingham, AL 35294

How does DT1 sphere perform in those who previously dropped out of contact lenses due to comfort or dryness?

Principal Investigator:

[name], OD, MS, FNAP, FAAO²

Additional Support:

[name], OD, MS³

[name], BS¹

[name], OD, PhD, FAAO²

[name], OD⁴

[name], OD, FAAO²

[name], OD, PhD, FAAO, FSLs, FBCLA¹

Southern College of Optometry²

[name]

Memphis, TN 38104

[contact]

University of Alabama at Birmingham¹

Birmingham, AL

Memphis, TN

ProCare Vision Center³

Granville, OH

Kannarr Eye Care⁴

Pittsburgh, KS

I. INTRODUCTION & RATIONALE

CL discomfort is a complex phenomenon that has been defined by the Tear Film and Ocular Surface Society in their seminal report on contact lens (CL) discomfort as a condition that results in “episodic or persistent adverse ocular sensation related to lens wear, either with or without visual disturbance resulting from reduced compatibility between the CL and the environment, which can lead to decreased wearing time and discontinuation of CL wear.”¹ A recent review by [name] and Tichenor found that CL discomfort was the top reason for established CL wears to cease wearing CLs.² This same review alarmingly found that the frequency of CL dropout was about 20% across the many studies aimed at evaluating this condition, which is surprising given the introduction of better soft CL materials and daily disposable CLs over the past 20 plus years.²

Dailies Total1 (DT1), which is a relatively new daily disposable CL, is a commonly used trouble shooting CL for patients who have failed with other CLs because DT1 utilizes advanced material technology that is specifically aimed at improving CL comfort. While DT1 is commonly used in these struggling patients, the literature currently lacks a targeted study aimed at understanding the frequency of successfully refitting CL dropouts into this advanced CL. Thus, the purpose of this study is to determine the frequency that past CL wearers who failed because of dryness or CL discomfort who can comfortable wear DT1.

II. SPECIFIC AIM

We plan to accomplish our goal by pursuing the following specific aim and testing the associated hypothesis:

Aim:

Determine the frequency of past CL wearers who failed because dryness or CL discomfort who can comfortably wear DT1. Hypothesis 1: At least 50% of past CL wearers can comfortably wear DT1 at one month (Positive Visual Analog Scale Score (VAS) based upon +50/50 VAS scale with 0 as neutral).

Exploratory Outcomes

A Likert questionnaire will be used to determine the following patient-reported outcomes at 1 and 6 months: 1. Likelihood of continuing to wear DT1, 2. Overall satisfaction while wearing DT1, Overall vision while wearing DT1, 3. End of day comfort while wearing DT1. The SPEED questionaries will also be used to determine the frequency of DT1 wears who can comfortable wear DT1 (scores ≤ 3).³

III. STUDY DESIGN

Participants

This 6-month, three-visit clinical study will be conducted at the University of Alabama at Birmingham (Birmingham, AL, USA), the Southern College of Optometry (Memphis, TN), and ProCare Vision Center (Granville, OH). One month will be the primary outcome timepoint because Young et al. found that most participants who dropped out of CLs in their study dropped out by 1 month (23% dropout).⁴ Participants will also be called at 6-months like in Young et al.’s study to determine the ultimate CL success frequency. This 6-month survey will be an exploratory outcome that will supported by the investigators (not Alcon). Participants will be recruited via clinic records, email, and fliers. Participants will be prescreened with an IRB approved phone script prior to the study visit to help determine if they qualify for the study. The reason why all potential participants dropped out of CLs will be recorded even if they are not included in the study. Adult, 18-

to 40-year-old, past CL wearers who have best corrected 20/20 visual acuity or better will be recruited. Participants will be required to have worn CLs for at least one year in the past. Participants over the age of 40 years will be excluded to avoid presbyopia-related vision issues. All participants will be required to have dropped out of CLs within the past two years because of discomfort or dryness. This determination will be made by listing Young et al.'s list of reasons for dropping out of CLs and asking the participants to indicate their top reason for dropping out of CLs: 1. Discomfort or Dryness, 2. General Poor Vision, 3. Poor Reading Vision, 4. Difficulty with Handling, 5. Advised by Practitioner, 6. Inconvenient, 7. Eyes were Red, 8. Lost Interest, 9. Too Costly, 10. Reaction to Care Products, 11. Lost Lenses, 12. Other.⁴ Participants will be considered a CL dropout if they have not worn CLs in the past 3 months. Participants will be required to have scores of ≤ 3 on the SPEED questionnaires (no significant dry eye symptoms).³ Participants will be required to be able to wear DT1 Sphere (astigmatism better than 0.75 D OD/OS). Participants will be required to provide a glasses prescription that is less than 3 years old. Participants will be excluded if they are past rigid CL wearers, have a past history of being diagnosed with dry eye or ocular allergies, have known systemic health conditions that are thought to alter tear film physiology, have a history of viral eye disease, have a history of ocular surgery, have a history of severe ocular trauma, have a history of corneal dystrophies or degenerations, have active ocular infection or inflammation, are currently using isotretinoin-derivatives or ocular medications, or if they are pregnant or breast feeding.⁵

Sample Size

This pilot study is proposing a sample of 60 participants (20/site) to estimate the initial frequency that participants can comfortably wear DT1 at 1 month. This sample size was selected because it is a feasible number of participants that can be recruited while also providing enough data to determine if at least 50% of participants can comfortable wear DT1 CLs. These should also be enough participants to evaluate exploratory patient reported outcomes such as the likelihood of continuing DT1 after completing the study. An additional 5 participants per site are being requested in case someone fails the glasses prescription requirements for this study. Additional participants will only be recruited if needed.

Surveys and Clinical Tests

Visit 1: Baseline

1. Participant History, Eligibility, Informed Consent: Participants will be asked to repeat the IRB approved screening survey at the study visit to verify that they are still eligible for the study. All participants will be screened with the SPEED questionnaire to understand their initial eye comfort (scores ≤ 3 required).⁶ The SPEED is being selected because it has been validated in both CL and non-CL wearers. All relevant patient demographics will be collected via a questionnaire developed by the investigators. Non-eligible participants will be dismissed at this time or rescheduled depending upon the reason for ineligibility. Eligible participants will be enrolled, consented, and requested to sign a privacy document.

2. Visual Acuity with Spectacles: Visual acuity will be measured with a Bailey-Lovie high-contrast chart.

3. Manifest Refraction: The investigator will determine the participants' refractive error with a phoropter, and binocular balance will be performed if best-corrected visual acuity is equal in between eyes. No more than 1.00 D of sphere will be added beyond the initial blur balance starting point.

4. Slit-Lamp Biomicroscopy: The investigator will use a slit-lamp biomicroscope to document normal and/or remarkable findings of the anterior eye structures: eyelashes (blepharitis), eyelids, conjunctiva, and cornea.

5. CL Fitting: Participants will be fit in DT1 sphere CLs. The CLs will be evaluated for centration, movement, coverage, and CL power adjustments will only be made if they improve Snellen visual acuity.

Visit 2: 1 Week

1. Stannard Patient Evaluation of Eye Dryness (SPEED): The SPEED questionnaire will be completed.

2. Visual Acuity with CLs: Visual acuity will be measured with a Bailey-Lovie high-contrast chart.

3. Slit-Lamp Biomicroscopy: The investigator will use a slit-lamp biomicroscope to document normal and/or remarkable findings of the anterior eye structures: eyelashes (blepharitis), eyelids, conjunctiva, and cornea.

4. CL Evaluation: The CLs will be evaluated for centration, movement, and coverage, and lens power adjustments will only be made if they improve Snellen visual acuity.

Visit 3: 1 Month (Primary Endpoint)

1. Stannard Patient Evaluation of Eye Dryness (SPEED): The SPEED questionnaire will be completed.

2. Visual Analog Scale (VAS): The VAS will be completed.

3. Investigator Survey: An exploratory questionnaire that probes topics such as vision, dryness, comfortable wear time, and willingness to continue wearing the contact lenses will be completed.

4. Visual Acuity with CLs: Visual acuity will be measured with a Bailey-Lovie high-contrast chart.

5. Slit-Lamp Biomicroscopy: The investigator will use a slit-lamp biomicroscope to document normal and/or remarkable findings of the anterior eye structures: eyelashes (blepharitis), eyelids, conjunctiva, and cornea.

6. CL Evaluation: The CLs will be evaluated for centration, movement, and coverage, and lens power adjustments will only be made if they improve Snellen visual acuity.

7. Study Completion: The participants will be compensated for their time, and they will be released from the clinical segment of the study. If participants like the CLs, they will be given a prescription for the CLs, though they will be required to buy their own CLs. The participants will also be educated that they will be called in 6 months to understand their wearing experience if they decide to continue wearing DT1 CLs.

Data Analysis

All data will be analyzed with Stata/IC 15 (StataCorp LLC; TX, USA). The frequency of participants who have comfortable VAS scores will be calculated at both the 1-month (primary outcome) and 6-month visits (exploratory outcome). The frequency of each Likert question and the SPEED will also be calculated.

Training of Study Personnel

Prior to enrolling any participants all examiners will participate in a training session developed by [name], OD, PhD. This full investigator meeting will ensure that all study investigators are performing the

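### Does the exploratory SPEED ≤ 3 outcome need a stated denominator and a rule for participants who stop DT1?

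*Combined protocol and SAP*

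**What the plan says.** All locations are in the combined protocol and SAP.

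- **II. Specific Aim, Exploratory Outcomes:** "The SPEED questionaries will also be used to determine the frequency of DT1 wears who can comfortable wear DT1 (scores ≤ 3"). The sentence names no timepoint, analysis set or count.
- **II. Specific Aim, Aim:** the main aim is worded over a different group: "Determine the frequency of past CL wearers who failed because dryness or CL discomfort who can comfortably wear DT1".
- **III. Study Design, Data Analysis:** the VAS result is a frequency of participants. The next sentence adds only that frequencies will be calculated for the Likert items and the SPEED.
- **III. Study Design, Visits 2 and 3:** SPEED is completed at 1 week and 1 month. There is no separate instruction for someone no longer wearing DT1.
- **III. Study Design, Participants:** "Participants will be required to have scores of ≤ 3 on the SPEED questionnaires (no significant dry eye symptoms"). At that point they are off lenses: "Participants will be considered a CL dropout if they have not worn CLs in the past 3 months".
- **III. Study Design, Visit 1:** the same cut-off is checked again, and on the choice of instrument the plan says: "The SPEED is being selected because it has been validated in both CL and non-CL wearers".
- **I. Introduction & Rationale:** the gap in the literature is described as "understanding the frequency of successfully refitting CL dropouts into this advanced CL".

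**The concern.** The sentence speaks of people who wear DT1, whereas the aim speaks of past lens wearers and the VAS analysis of participants. Read literally, the SPEED percentage covers only those still in the lens. Anyone who gave up would drop out of both numerator and denominator, and the result could be mistaken for the share of refitted dropouts who wear DT1 comfortably.

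A second reading looks worse. Everyone must score 3 or less off lenses to enter, and the same cut-off later stands for comfortable DT1 wear. If every attendee is tabulated, a participant who quit, went back to glasses and returned to the entry score would count as a success. SPEED can be completed by non-wearers, so the instrument does not prevent this.

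At stake is whether the plan's second measure of comfort could be reported higher than the share of all fitted participants who are both wearing DT1 and comfortable.

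**Working it through.** **Figures in the plan.** The plan gives no number for the SPEED outcome. The only figure to reproduce is the sample size: 20 per site × 3 sites = 60, which agrees with Sample Size.

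**Inputs**

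- N = 60 fitted (Sample Size).
- D = number who stop by 1 month. Assumed: 6 (10%) or 14 (23% × 60 = 13.8, rounded). The 23% is the dropout in the lapsed-wearer study cited under Participants; the plan does not adopt it as its own rate.
- K = continuing wearers scoring 3 or less. Assumed: 32 of 54, or 28 of 46 (about 60%).
- A = stoppers who attend; Q = those among them scoring 3 or less. Both are unknown, so their ranges are shown.
- All continuing wearers are assumed to attend.

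**Formulas**

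- Wearers only: K / (N − D)
- All fitted, stoppers counted as not comfortable: K / N
- All attendees: (K + Q) / (N − D + A)

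**Results**

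| Reading | D = 6, K = 32 | D = 14, K = 28 |
|---|---|---|
| Wearers only | 32/54 = 59.3% | 28/46 = 60.9% |
| All fitted, stoppers as failures | 32/60 = 53.3% | 28/60 = 46.7% |
| All attendees, lowest (all stoppers attend, none ≤ 3) | 32/60 = 53.3% | 28/60 = 46.7% |
| All attendees, highest (all stoppers attend, all ≤ 3) | 38/60 = 63.3% | 42/60 = 70.0% |

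Wearers only exceeds all fitted by 5.9 points with 6 stopping and by 14.2 points with 14 stopping. If only 7 of the 14 stoppers attend, the attendee figure runs from 28/53 = 52.8% to 35/53 = 66.0%.

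**Which way the error runs.** Wearers only is always the larger figure when stoppers are counted as failures, but that convention is not in the plan. If the target is comfort in the lens, 60.9% holds for all 60 when 14 × 28/46 = 8.5 of the 14 stoppers were comfortable in DT1. With more than that it is too low; with fewer it is too high.

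**What the all-fitted rule costs.** Suppose 4 of the 14 stopped for other reasons while comfortable. Comfort is then (28 + 4)/60 = 53.3%, and the all-fitted rule reports 46.7%, which is 6.7 points too low.

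**The wording.** Every enrolled participant is fitted with DT1 at Visit 1, so the phrase in the SPEED sentence can also mean everyone fitted. Data Analysis places SPEED directly after a frequency of participants, which fits that reading. The text therefore does not settle on continuing wearers.

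**The case for a change.** The best case for a change is this. The omission is a fact: no section gives SPEED a denominator or a rule for those who stop. Stopping is what the study exists to observe, and 1 month was chosen because the cited study lost most of its dropouts by then. The entry cut-off and the success cut-off are identical, so an off-lens score has no value as evidence of comfortable DT1 wear. In the illustration with 14 stopping, the choice of denominator moves the result across 50%. One sentence in each of two sections would settle it.

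The omission stands, and so does the point about off-lens scores. The rest is weaker.

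- The 50% benchmark belongs to the VAS hypothesis; no threshold is attached to the SPEED frequency.
- It is tempting to argue that stoppers must be less comfortable because "All participants will be required to have dropped out of CLs within the past two years because of discomfort or dryness". That history is shared by everyone enrolled, so it cannot separate stoppers from continuers.
- The ends of the 46.7% to 70.0% range need every stopper to attend and all of them to score the same way.
- The silence is not particular to SPEED. Data Analysis gives no rule for stoppers or missing participants for the 1-month VAS either. Fixing a stoppers-fail rule for SPEED alone would put the two comfort measures on different bases.
- SPEED is not asked to measure refitting success alone. The VAS carries the hypothesis, the 6-month call addresses eventual success, and likelihood of continuing is a separate Likert item.
- The Visit 3 survey already asks about comfortable wearing time and willingness to carry on. Its items are not reproduced, so a missing wear-status item cannot be shown.

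**Conclusion.** No change to the plan is needed. What remains is missing detail on one exploratory, descriptive percentage in a pilot of 60. A wearers-only frequency is a legitimate quantity and matches the sentence as written; shown with its n beside the number fitted, it misleads nobody. Counting a person back in glasses as comfortable in DT1 would be wrong, but the plan does not say to do so, and an analyst tabulating comfort in a lens would not use a score obtained without it.

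Scoring success as still wearing and SPEED ≤ 3 over all fitted would turn a symptom score into a composite of wear, comfort and attendance. That is a different estimand with its own bias, 6.7 points downward in the example, and not a correction of an error.

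The differences of 5.9 and 14.2 points rest wholly on assumed stopping rates and scores. They show what the choice of denominator could do, not a bias in the plan. This conclusion covers SPEED only; it does not imply that the primary VAS frequency has a rule for stoppers, because the plan states none there either.

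### SPEED ≤ 3 is both the off-lens entry criterion and the exploratory definition of comfortable DT1 wear, so its frequency can show maintenance on lens but not improvement or a DT1-specific benefit

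*Combined protocol and SAP*

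**What the plan says.** The same SPEED cut appears in two roles.

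- **Entry.** Section III, Participants: "Participants will be required to have scores of ≤ 3 on the SPEED questionnaires (no significant dry eye symptoms"). Visit 1, item 1, repeats the check: "All participants will be screened with the SPEED questionnaire to understand their initial eye comfort (scores ≤ 3 required"). Lens fitting comes later in that visit, as item 5.
- **Outcome.** Section II, Exploratory Outcomes: "The SPEED questionaries will also be used to determine the frequency of DT1 wears who can comfortable wear DT1 (scores ≤ 3").

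The entry score is an off-lens score. Participants says: "Participants will be considered a CL dropout if they have not worn CLs in the past 3 months". The earlier failure was on lens: "All participants will be required to have dropped out of CLs within the past two years because of discomfort or dryness".

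SPEED is completed again at 1 week and at 1 month. For its analysis, Data Analysis says only: "The frequency of each Likert question and the SPEED will also be calculated". It mentions no change from Visit 1, no interval and no benchmark for SPEED, and the design has no comparison lens.

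The primary outcome is a different measure: "At least 50% of past CL wearers can comfortably wear DT1 at one month (Positive Visual Analog Scale Score (VAS").

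**The concern.** When a success definition is also an entry criterion, everyone is a success before treatment starts. A report that most participants can comfortably wear DT1 by SPEED would then be describing, in part, who was let in. The frequency has no room to rise, so it cannot reveal improvement. People selected for a low score also tend to score somewhat higher at retest, so some would cross the cut even if the lens had no effect.

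What is at stake is how one exploratory result is read. Take a 1-month figure of 80%. Reported alone, it looks like a success rate. Set against its starting point, it means that 12 of 60 people without significant symptoms off lens had moved above the cut. The planned summary does not bring that out, and does not separate selection from a lens effect.

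**Working it through.** **Inputs from the documents.** Entry cut ≤ 3; outcome cut ≤ 3; sample 20 per site at three sites, 3 × 20 = 60, which agrees with the stated 60. The plan gives no SPEED frequency, target or power, so there is no planned SPEED result to reproduce.

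**Step 1: starting value.** Share at or below the cut at entry = 60/60 = 100%, by selection.

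**Step 2: expected follow-up frequency.** The documents give no SPEED distribution or retest reliability, so the following are assumptions: bivariate normal scores in the candidate pool, a share q = 0.5 to 0.8 of candidates at or below the cut, test-retest correlation r = 0.7 to 0.9, and a lens effect that raises all follow-up scores by d standard deviations (SD of the candidate pool). With c = Φ⁻¹(q):

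P(follow-up ≤ cut | entry ≤ cut) = Φ₂(c, c − d; r) / q

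| q | r | d = 0 | d = 0.5 | d = 1 |
|---|---|---|---|---|
| 0.5 | 0.7 | 74.7% | 51.9% | 29.1% |
| 0.5 | 0.9 | 85.6% | 59.4% | 31.6% |
| 0.7 | 0.7 | 84.4% | 65.9% | 43.1% |
| 0.7 | 0.9 | 91.1% | 71.2% | 45.2% |
| 0.8 | 0.7 | 89.1% | 74.0% | 52.9% |
| 0.8 | 0.9 | 93.7% | 78.0% | 54.5% |

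With no lens effect, 100 − 93.7 = 6.3% to 100 − 74.7 = 25.3% move above the cut. That is 0.063 × 60 ≈ 4 to 0.253 × 60 ≈ 15 participants. A wider set of assumptions (q = 0.3 to 0.7, r = 0.5 to 0.9) gives 52% to 91% still at or below the cut with no lens effect, and 15% to 45% with a 1 SD worsening.

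**Step 3: what the frequency alone can separate.** Under the first set of assumptions, the range for no lens effect (74.7% to 93.7%) overlaps the range for a 0.5 SD worsening (51.9% to 78.0%). It does not overlap the range for a 1 SD worsening (29.1% to 54.5%). The measure therefore responds to the lens, but a modest worsening cannot be told from selection alone without knowing q and r.

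**Step 4: what the paired change adds.** In the same model the expected mean change is (1 − r) φ(c)/q + d, in SD units. With d = 0:

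- q = 0.5, r = 0.7: 0.3 × 0.399/0.5 = 0.24
- q = 0.8, r = 0.9: 0.1 × 0.280/0.8 = 0.035

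Selection alone thus gives a rise of about 0.04 to 0.24 SD. Adding 0.5 gives about 0.54 to 0.74 SD. These two ranges do not overlap, whereas the two frequency ranges do. The paired change is still exposed to selection, but less ambiguous.

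**Step 5: precision at n = 60.** Exact (Clopper-Pearson) 95% intervals: 54/60 = 90%, 79.5% to 96.2%; 48/60 = 80%, 67.7% to 89.2%. The complement of the latter, 12/60 = 20%, has the interval 10.8% to 32.3%.

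**The case against.** The aim is whether people who gave up lenses for discomfort or dryness can wear DT1 comfortably. It is not whether their symptoms improve. The 100% at entry is an off-lens state, and nobody has yet worn DT1. Requiring no significant symptoms off lens and then asking whether people stay that way on lens is a coherent tolerability question. The plan also gives a reason for using one instrument in both states: "The SPEED is being selected because it has been validated in both CL and non-CL wearers". All of this stands.

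It rules out several stronger readings that a reader might infer:

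- *A high SPEED frequency cannot support DT1 at all, or would be high whatever the lens does.* The table shows otherwise: with q and r held in the same ranges, a 1 SD worsening takes 74.7%–93.7% down to 29.1%–54.5%. A high value is evidence against substantial induced symptoms.
- *The SPEED frequency is a test of the 50% hypothesis.* That hypothesis is defined on a positive VAS. No target is attached to SPEED.
- *The plan discards the Visit 1 score.* The Data Analysis sentence names no visit for SPEED and does not exclude baseline. It is silent on change.

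A further objection is that counting moves from ≤ 3 to > 3 adds little. Since everyone starts at ≤ 3, that count is the complement of the planned frequency among those assessed. This is right. The useful additions are the paired change, the intervals and the label.

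**Conclusion.** The point holds in a limited form. Because the cut is the same at entry and at follow-up, the SPEED frequency starts at 100% by selection and can show only maintenance on lens. It cannot show improvement, nor, without a comparison lens, an effect specific to DT1. That much follows from the text and needs no assumption.

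The size of the expected drift with no lens effect, about 6% to 25% of participants above 3, rests on assumed pass rates, retest correlations and normality. A questionnaire score will follow the normal model only roughly, and the wider assumptions above shift the range, so neither range is a property of this trial. Low priority: the outcome is exploratory, the study calls itself a pilot, and the primary endpoint does not depend on SPEED.

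**What to change.** In Data Analysis, extend the sentence on SPEED as follows:

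1. Report the paired mean change in SPEED from Visit 1 to 1 week and to 1 month, each with a 95% CI.
2. Report the follow-up frequency with an exact 95% CI, labelled *remained without significant symptoms (SPEED ≤ 3) on lens*, and state beside it that all participants met this cut off lens at entry.
3. Note that part of any rise in score, and part of any fall in the frequency, reflects selection on a low entry score.

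Use the same label under Exploratory Outcomes. The cost is a few lines of Stata on scores already collected at Visits 1, 2 and 3, with no new data and no added burden on participants.

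### The exploratory 6-month result cannot separate comfort lost after 1 month from stopping for cost or other reasons, because lenses must then be bought and no reason for stopping is described

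*Combined protocol and SAP*

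**What the plan says.** The Specific Aim concerns comfort: how often people who gave up lenses because of dryness or discomfort can wear DT1 comfortably. Hypothesis 1 sets that at 1 month, as at least 50% with a positive VAS.

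The 6-month follow-up is described in four places:

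- **Study Design, Participants.** Participants are called at 6 months "to determine the ultimate CL success frequency". The same paragraph labels this survey exploratory.
- **Visit 3, item 7 (Study Completion).** Participants leave the clinical segment at 1 month. If they like the lenses, "they will be given a prescription for the CLs, though they will be required to buy their own CLs". They are also told that "they will be called in 6 months to understand their wearing experience if they decide to continue wearing DT1 CLs".
- **Exploratory Outcomes.** "A Likert questionnaire will be used to determine the following patient-reported outcomes at 1 and 6 months": likelihood of continuing, satisfaction, vision and end-of-day comfort. SPEED is added without a stated time point.
- **Data Analysis.** "The frequency of participants who have comfortable VAS scores will be calculated at both the 1-month (primary outcome) and 6-month visits (exploratory outcome". Likert and SPEED frequencies are also to be calculated.

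Reasons for giving up lenses appear only at entry. Eligibility is settled by "asking the participants to indicate their top reason for dropping out of CLs" from a 12-item list that ends "8. Lost Interest, 9. Too Costly, 10. Reaction to Care Products, 11. Lost Lenses, 12. Other".

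**The concern.** The need to buy lenses begins exactly where the 1-to-6-month interval begins. Any fall in wear or in comfortable wear over that interval has at least two possible causes: the lenses became uncomfortable, or the participant did not want to pay or stopped for some other reason. The protocol treats this distinction as decisive at entry, since it admits only people whose top reason was discomfort or dryness. It does not describe asking the same question when an enrolled participant stops again.

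At stake is the meaning of the 6-month number. Readers will take a figure described as ultimate success, in a study about comfort, as saying how many former dropouts remain comfortable in DT1. The described data cannot support that reading, and the answers may be unrecoverable once the calls have been made.

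**Working it through.** **The plan's own figure.** The only design figure is N = 60. It agrees with 3 named sites × 20 = 60. No alpha, power or 6-month rate is given, so there is nothing further to reproduce. The point rests on reading the sections together; the arithmetic only shows scale.

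**Step 1: what is defined at 6 months.** The documents give no definition of 6-month success, no denominator and no rule for people no longer wearing DT1. Two readings are open:

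- *Reading A.* All participants are followed up and a non-wearer is not a success. This fits the stated purpose in Study Design.
- *Reading B.* Only those who carry on wearing DT1 are asked about their experience. This fits the conditional wording in Study Completion.

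**Step 2: an illustration.** Inputs:

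- N = 60 (Sample Size).
- Loss by 1 month of 23%, the early dropout quoted from the cited study of lapsed wearers, borrowed here as an assumption: 60 × (1 − 0.23) = 46.2, taken as 46 wearing at 1 month.
- Of those 46, 10% stop later for discomfort (4.6, taken as 5). This is an assumption.
- Of those 46, 0%, 10%, 20% or 30% stop for cost or other reasons (0, 5, 9 or 14 people). This is also an assumption; the documents give no rate.

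Still wearing = 46 − 5 − other stops. Without a discomfort failure after 1 month = still wearing + other stops. The 14 people gone by 1 month count against success throughout, and continuing wearers are taken as comfortable.

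| Stop for cost or other | Still wearing | Reading A: still wearing / 60 | No discomfort failure after 1 month / 60 |
|---|---|---|---|
| 0 | 41 | 68% | 41/60 = 68% |
| 5 | 36 | 60% | 41/60 = 68% |
| 9 | 32 | 53% | 41/60 = 68% |
| 14 | 27 | 45% | 41/60 = 68% |

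The Reading A figure falls from 68% to 45% while comfort does not change.

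**Step 3: Reading B on the second row.** Only the 36 continuing wearers are asked. If all have a positive VAS, the figure is 36/36 = 100%, against 60% on Reading A and 68% in the last column. The same participants give answers on either side of the comfort result, depending on a rule the plan does not state.

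**Step 4: what the planned data leave open.** Suppose only the totals are known: 46 wearing at 1 month and 36 at 6 months. Then 46 − 36 = 10 people stopped for unknown reasons.

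- All 10 for discomfort: 36/60 = 60%.
- None for discomfort: (36 + 10)/60 = 46/60 = 77%.

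The gap is 10/60, or about 17 percentage points. It is not sampling error, and a larger sample would not remove it. The 95% Clopper-Pearson interval for 36/60, which is 46.5% to 72.4%, comes on top of it.

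**The case against.** The strongest reply is that this is an exploratory telephone follow-up. The hypothesis is tested on the 1-month VAS, before anyone has to buy lenses as part of carrying on, so the main question is answered elsewhere. That stands, and it limits the point to how the 6-month result is read.

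A second reply is that wearing lenses one has paid for is a fair practical test, and lasting success can reasonably include willingness to pay. That also stands. Continuation is worth reporting, but it is a different quantity from comfort and should be labelled as such.

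Third, the 1-month data help. Everyone who completes Visit 3 has a VAS, SPEED and a survey covering comfortable wear time and willingness to continue. A reader might infer that a comfortable person who did not buy lenses cannot be told from a comfort failure at all. That goes too far: someone already uncomfortable at 1 month can be identified. What stays unresolved is comfort lost afterwards.

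Fourth, the call script is not in the document and may ask for reasons. The supportable statement is that no such question is described, not that none will be asked. Similarly, study supply of lenses up to 1 month is implied by the later need to buy them, not stated.

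**Conclusion.** The point holds as a limit on the exploratory 6-month result. As described, that result cannot separate comfort lost after 1 month from stopping for cost or other reasons, and the direction of the error depends on an unstated rule: too low as a measure of comfort if non-wearers count as failures, and tending to be too high if only continuing wearers are asked. In the illustration the unresolved range is 60% to 77%. Its width depends on assumed numbers of stoppers; that a range exists does not.

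Three stronger conclusions that a reader might draw are not supported:

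- *The primary result is compromised.* It is not; it is read at 1 month.
- *Stops for cost could make the study miss its 50% target.* That target belongs to the 1-month VAS, and nothing in the documents applies it at 6 months.
- *The plan counts non-wearers as failures.* No section says so, and the Study Completion wording can be read the other way.

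The change is worth making because it is cheap and decides what the 6-month analysis can conclude. It is not essential to the validity of the trial.

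**What to change.** 1. State that all fitted participants are called at 6 months, whether or not they still wear DT1.
2. Ask anyone no longer wearing DT1 for their top reason, using the existing 12-item screening list, and for the date they stopped. The date separates stops before and after the 1-month visit.
3. In Data Analysis, use all fitted participants as the denominator and report five groups: (a) still wearing, positive VAS; (b) still wearing, VAS not positive; (c) stopped for discomfort or dryness; (d) stopped for another reason, with cost shown separately; (e) not reached.
4. Report continuation (a + b) as one result and comfort failure (b + c) as another. Group (b) has to count as comfort failure, because the protocol defines comfort by a positive VAS and not by continued wear.

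The cost is a few more calls, two extra questions and one extra table. Lens supply, sample size and the primary endpoint do not change. If the call script already asks for reasons, only who is called and the reporting rule need to be written down. One limit remains: a single self-reported top reason will not fully separate people who stopped for both comfort and cost.
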